9.2.3 Administration

Administer the infusion over 60 minutes through an intravenous line containing a sterile, non-pyrogenic, low protein binding in-line filter (pore size of 0.2 micrometer to 1.2 micrometer). Do not co-administer other drugs through the same intravenous line.

Flush the intravenous line at end of infusion.

9.3 Dose Modifications

Recommendations for nivolumab modifications are provided in Table 1. There are no recommended dose modifications for hypothyroidism or hyperthyroidism.

Interrupt or slow the rate of infusion in patients with mild or moderate infusion reactions. Discontinue nivolumab in patients with severe or life-threatening infusion reactions. Please refer to Table below for Recommended Dose Modifications.

Adverse Reaction	Severity*	Dose Modifications
Colitis	Grade 2 diarrhea or colitis	Withhold dose ^a
	Grade 3 diarrhea or colitis	Withhold dose ^a when administered as a single agent
	Grade 4 diarrhea or colitis	Permanently discontinue when administered with ipilimumab Permanently discontinue
Pneumonitis	Grade 2 pneumonitis	Withhold dose ^a
	Grade 3 or 4 pneumonitis	Permanently discontinue
Hepatitis	Aspartate aminotransferase (AST)/or alanine aminotransferase (ALT) more than 3 and up to 5 times the upper limit of normal or total bilirubin more than 1.5 and up to 3 times the upper limit of normal	Withhold dose
	AST or ALT more than 5 times the upper limit of normal or total bilirubin more than 3 times the upper limit of normal	Permanently discontinue
Hypophysitis	Grade 2 or 3 hypophysitis	Withhold dose ^a
	Grade 4 hypophysitis	Permanently discontinue
Adrenal Insufficiency	Grade 2 adrenal insufficiency	Withhold dose ^a
	Grade 3 or 4 adrenal insufficiency	Permanently discontinue
Type 1 Diabetes Mellitus	Grade 3 hyperglycemia	Withhold dose ^a
	Grade 4 hyperglycemia	Permanently discontinue
Nephritis and Renal Dysfunction	Serum creatinine more than 1.5 and up to 6 times the upper limit of normal	Withhold dose ^a
	Serum creatinine more than 6 times the upper limit of normal	Permanently discontinue

Rash	Grade 3 rash	Withhold dose ^a
	Grade 4 rash	Permanently discontinue
Encephalitis	New-onset moderate or severe neurologic signs or symptoms	Withhold dose ^a
	Immune-mediated encephalitis	Permanently discontinue
Other	Other Grade 3 adverse reaction First occurrence	Withhold dose ^a
	Recurrence of same Grade 3 adverse reactions	Permanently discontinue
	Life-threatening or Grade 4 adverse reaction	Permanently discontinue
	Requirement for 10 mg per day or greater prednisone or equivalent for more than 12 weeks	Permanently discontinue
	Persistent Grade 2 or 3 adverse reactions lasting 12 weeks or longer	Permanently discontinue

^a Resume treatment when adverse reaction returns to Grade 0 or 1.

* Toxicity was graded per National Cancer Institute Common Terminology Criteria for Adverse Events, Version 4.0 (NCI CTCAE v4).

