Immune-mediated colitis, defined as requiring use of corticosteroids with no clear alternate etiology, can occur with nivolumab treatment. Monitor patients for signs and symptoms of colitis. Administer corticosteroids at a dose of 1 to 2 mg/kg/day prednisone equivalents followed by corticosteroid taper for severe (Grade 3) or life-threatening (Grade 4) colitis. Administer corticosteroids at a dose of 0.5 to 1 mg/kg/day prednisone equivalents followed by corticosteroid taper for moderate (Grade 2) colitis of more than 5 days duration; if worsening or no improvement occurs despite initiation of corticosteroids, increase dose to 1 to 2 mg/kg/day prednisone equivalents. When administered as a single agent, withhold nivolumab for moderate or severe (Grade 2 or 3) colitis. Permanently discontinue nivolumab for life-threatening (Grade 4) or for recurrent colitis upon restarting nivolumab.

In patients with RCC, diarrhea or colitis occurred in 25% (100/406) of patients receiving nivolumab and 32% (126/397) of patients receiving everolimus. Immune-mediated diarrhea or colitis occurred in 3.2% (13/406) of patients receiving nivolumab (five patients with Grade 3, seven with Grade 2, and one with Grade 1). The median time to onset was 4.8 months (range: 2 days to 15.6 months). The median duration was 1.3 months (range: 0.2 to 3.9 months).

1.5.1.6.3 3.6.3 Immune-Mediated Hepatitis

Immune-mediated hepatitis, defined as requiring use of corticosteroids and no clear alternate etiology, can occur with nivolumab treatment. Monitor patients for abnormal liver tests prior to and periodically during treatment. Administer corticosteroids at a dose of 0.5 to 1 mg/kg/day prednisone equivalents for moderate (Grade 2) transaminase elevations, with or without concomitant elevation in total bilirubin. Administer corticosteroids at a dose of 1 to 2 mg/kg/day prednisone equivalents for severe (Grade 3) or life-threatening (Grade 4) transaminase elevations, with or without concomitant elevation in total bilirubin. Withhold nivolumab for moderate (Grade 2) and permanently discontinue nivolumab for severe (Grade 3) or life-threatening (Grade 4) immune-mediated hepatitis

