1.5.1.6.11 3.6.6 Immune-Mediated Rash

Immune-mediated rash can occur with nivolumab treatment. Severe rash (including rare cases of fatal toxic epidermal necrolysis) occurred in the clinical program of nivolumab. Monitor patients for rash. Administer corticosteroids at a dose of 1 to 2 mg/kg/day prednisone equivalents for severe (Grade 3) or life-threatening (Grade 4) rash. Withhold nivolumab for severe (Grade 3) rash and permanently discontinue nivolumab for life-threatening (Grade 4) rash.

In RCC, rash occurred in 28% (112/406) of patients on nivolumab and 36% (143/397) of patients on everolimus. Immune-mediated rash, defined as a rash treated with systemic or topical corticosteroids, occurred in 7% (30/406) of patients receiving nivolumab (four with Grade 3, seven with Grade 2, and nineteen with Grade 1). The median time to onset was 3.2 months (range: 2 days to 25.8 months). Median duration was 2.6 months (range: 0.3 to 9.4 months).

1.5.1.6.12 3.6.7 Immune-Mediated Encephalitis

Immune-mediated encephalitis can occur with nivolumab treatment. Withhold nivolumab in patients with new-onset moderate to severe neurologic signs or symptoms and evaluate to rule out infectious or other causes of moderate to severe neurologic deterioration. Evaluation may include, but not be limited to, consultation with a neurologist, brain MRI and lumbar puncture. If other etiologies are ruled out, administer corticosteroids at a dose of 1 to 2 mg/kg/day prednisone equivalents for patients with immune-mediated encephalitis, followed by corticosteroid taper. Permanently discontinue nivolumab for immune-mediated encephalitis

1.5.1.6.13 3.6.8 Other immune-mediated adverse reactions

Other clinically significant immune-mediated adverse reactions can occur with nivolumab. Immune-mediated adverse reactions may occur after discontinuation of nivolumab therapy. For any suspected immune-mediated adverse reactions, exclude other causes. Based on the severity of the adverse reaction, permanently discontinue or withhold nivolumab, administer high-dose corticosteroids, and if appropriate, initiate hormone-replacement therapy. Upon improvement to Grade 1 or less, initiate corticosteroid taper and continue to taper over at least 1 month. Consider restarting nivolumab after completion of corticosteroid taper based on the severity of the event.

1.5.1.6.14 3.6.9 Infusion Reactions

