13.0 Prohibited and Restricted therapies during the Study

13.1 Prohibited Therapies

Patients in this study may not use vaccines for the treatment of cancer or prevention of disease unless indicated as a component of the protocol regimen (including those for common medical conditions) for up to one month pre and post dosing with nivolumab or atezolizumab. Concomitant systemic or local anti-cancer medications or treatments are prohibited in this study while receiving nivolumab/atezolizumab treatments.

Patients may not use any of the following therapies during the study:

- Any non-study anti-cancer agent (investigational or non-investigational);
- Any other investigational agents; Any other PD-1 or PDL-1 inhibitors;
- Immunosuppressive agents;
- Chronic systemic corticosteroids;

[figure not shown]
- Any non-oncology vaccine therapies used for the prevention of infectious diseases (for up to 30 days prior to or after any dose of study drug).

CONFIDENTIAL

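### The nivolumab dose table in 9.3 has no row for recurrent Grade 2 colitis, so it falls under withhold and resume, while 3.6.2 stops nivolumab permanently for any recurrent colitis

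*Combined protocol and SAP*

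**What the plan says.** The protocol deals with colitis on nivolumab in two places.

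- **Section 9.3 (dose-modification table).** Grade 2 diarrhea or colitis is a withheld dose carrying footnote a: "Resume treatment when adverse reaction returns to Grade 0 or 1". The row does not separate a first episode from a later one. The table has one recurrence row, "Recurrence of same Grade 3 adverse reactions", which leads to permanent discontinuation. It sits among the rows for other reactions and is limited to Grade 3. A further row stops treatment for Grade 2 or 3 reactions that persist for 12 weeks or longer.
- **Section 3.6.2 (immune-mediated colitis).** A Grade 2 or 3 colitis on single-agent nivolumab is withheld, as in the table. The section then adds: "Permanently discontinue nivolumab for life-threatening (Grade 4) or for recurrent colitis upon restarting nivolumab". No grade is attached to the recurrence.

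Section 27.2 says that the study will also follow the dose-modification tables for holding therapy or permanently withdrawing patients. It cites them as 9.6 and 10.4, but the tables stand in 9.3 and 10.3. It also leaves resumption or withdrawal to the principal investigator's discretion. Section 17.2 lists unacceptable toxicity and physician's discretion among the reasons to stop the drug.

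**The concern.** The table is what a treating physician will consult, and it is the text to which 27.2 sends the study. On recurrent Grade 2 colitis it leads to a less cautious action than the protocol's own safety section. A physician who works from the table alone can re-treat a patient whom 3.6.2 would take off nivolumab for good. Nothing in the protocol says which section prevails.

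What is at stake is patient safety and consistent handling across patients. Nothing suggests an effect on the primary endpoint or on the comparison of arms, since both arms receive the same immunotherapy under the same table.

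**Working it through.** **Text comparison.** The plan states no figure on this point, so the first check is to set the two rules side by side. The Grade 3 recurrence row is taken to cover colitis, which is the reading that favours the table.

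| Situation | 9.3 table | 3.6.2 | Agree? |
|---|---|---|---|
| First Grade 2 colitis | Withhold, resume at Grade 0 or 1 | Withhold | Yes |
| Grade 4 colitis | Permanent stop | Permanent stop | Yes |
| Grade 3, then Grade 3 again after restart | Permanent stop | Permanent stop | Yes |
| Grade 2, then Grade 2 again after restart | Withhold, resume at Grade 0 or 1 | Permanent stop | **No** |
| Grade 3, then Grade 2 after restart | Withhold, resume at Grade 0 or 1 | Permanent stop | **No** |

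The 12-week persistence row does not close the gap, because it concerns a reaction that fails to resolve. A recurrence follows a resolution and a restart.

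**Inputs for size.**
- Grade 2 immune-mediated diarrhea or colitis in renal patients on nivolumab: 7 of 406 (section 3.6.2). Grade 3: 5 of 406 (same place).
- Renal patients in this trial: 56, assumed as half of 112. Section 29.0 expects about 20 patients per year in each cohort, which fits an even split, but no cohort size is fixed.
- Recurrence after restart: not in the documents. Assumed range 10% to 50%, with every patient restarting.

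**Step 1: first Grade 2 events.**
- Rate: 7/406 = 1.72% (exact 95% CI 0.70% to 3.52%).
- Expected number: 56 × 7/406 = 0.97.
- Chance of at least one: 1 − (1 − 7/406)^56 = 0.62. This is the chance of a first event, not of the conflict.

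**Step 2: patients who meet the conflict.** With recurrence probability r, the expected number is 56 × (7/406) × r. The chance of at least one is 1 − (1 − (7/406) × r)^56.

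| r (assumed) | Expected patients | Chance of at least one |
|---|---|---|
| 10% | 0.10 | 9% |
| 30% | 0.29 | 25% |
| 50% | 0.48 | 38% |

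**Step 3: sensitivity to a first Grade 3 episode.** Counting first events of Grade 2 or 3 gives (7 + 5)/406 = 12/406 = 3.0%, and 56 × 12/406 = 1.66 patients. If 10% to 50% of these had a Grade 2 recurrence, the expected number would be 1.66 × 0.10 = 0.17 to 1.66 × 0.50 = 0.83.

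**The case against.** The strongest reply is that the table is incomplete rather than opposed to 3.6.2. It does not expressly order re-treatment after a recurrent Grade 2 colitis; that result comes from joining the Grade 2 row to footnote a. Section 3.6.2 is built the same way, with a general rule to withhold and a specific stop for recurrence, and a careful reader could let the specific rule supplement the table. Section 9.3 calls its entries recommendations, and 27.2 adds the tables to investigator discretion. Nothing compels re-treatment.

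This is correct as far as it goes, and it keeps the point modest. It does not remove the point. Discretion allows a stop, whereas 3.6.2 requires one, and neither 27.2 nor 17.2 supplies a recurrence rule.

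A reader might also infer a second conflict: that footnote a allows dosing during a steroid taper which the protocol says must finish first. Section 3.6.8 does say "Upon improvement to Grade 1 or less, initiate corticosteroid taper and continue to taper over at least 1 month" and then speaks of considering a restart after the taper. The documents do not support a firm conflict here. The section is headed "3.6.8 Other immune-mediated adverse reactions" and opens with other reactions, although one sentence is worded more widely: "For any suspected immune-mediated adverse reactions, exclude other causes". Colitis, pneumonitis and nephritis each have their own subsection, and the restart sentence is advisory and depends on severity. Requiring a completed taper of at least one month for every footnote-a reaction would go beyond the protocol's text and is a debatable clinical trade-off.

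**Conclusion.** The point holds for recurrent colitis at Grade 2, whether the first episode was Grade 2 or Grade 3. For these cases the 9.3 table leads to withhold and resume, and 3.6.2 to permanent discontinuation. Grade 4 colitis and a repeated Grade 3 colitis can be reconciled.

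The expected size is about 0.1 to 0.5 patients, with roughly a 9% to 38% chance that at least one patient meets the conflict. This rests on several assumptions:
- 56 renal patients, and recurrence of 10% to 50% with all patients restarting.
- The cited rate, from 3 mg/kg dosing, carries over to the 240 mg flat dose with or without radiotherapy.
- All seven cited events count as colitis. The source figure is diarrhea or colitis, so the true number may be lower.
- Nivolumab is given to renal patients only. Section 6.2 also allows it in urothelial cancer, which would add an unknown number, as would Grade 2 recurrence after a first Grade 3 episode.

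This is a small but specific safety inconsistency that should be corrected. It is not evidence that the protocol permits dosing on steroids in breach of its own rules, nor that the efficacy analysis is affected.

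**What to change.** In the colitis rows of the 9.3 table, add: *Recurrent colitis of any grade upon restarting nivolumab: permanently discontinue.* In 27.2, correct the table references from 9.6 and 10.4 to 9.3 and 10.3, which is clerical. Leave footnote a as it stands.

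The cost is one table row and one cross-reference, with no added visits or tests. The downside is a permanent stop for the few patients with a recurrent Grade 2 colitis, which 3.6.2 already requires.

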10.0 Study Therapy [Atezolizumab]

10.1 Atezolizumab

Atezolizumab is an Fc-engineered, humanized, monoclonal antibody that binds to PD-L1 and blocks interactions with the PD-1 and B7.1 receptors. Atezolizumab is a non-glycosylated IgG1 kappa immunoglobulin that has a calculated molecular mass of 145 kDa.

In Arm A:

Patients with Urothelial cancer will receive either Nivolumab on Days* 1, 15, 29, 43 and 57 or Atezolizumab or Pembrolizumab on Days* 1, 22, 43, 64

(* - infusions will have a ± 3 days window to accommodate inevitable scheduling changes and holidays)

In Arm B:

Radiation is given to one lesion, 30 Gy in 3 fractions of 10 Gy each, over one week interval (with a minimum of 36 hours between each fraction), conformally or by intensity modulated radiation treatment to maximally spare normal tissue.

On the day of radiation (Day 1) immunotherapy is administered and repeated on the scheduled days. Patients will receive radiation on Day 1 and immunotherapy will be given ± 24 hr from Day 1.

Patients on both treatment arms will undergo re-imaging on Day 63 (± 7 days) (after completing 5 (after completing 4 doses of Atezolizumab) and every 9 weeks (± 7 days) for one year and every 12 weeks (± 7 days) thereafter.

The first dose will be administered on Day 1 (± 24 hrs) and repeated on Days 15, 22, 43 and 64. Radiation will be delivered every other day (with a minimum of 36 hours between each fraction), starting on Day 1. A dose of 10 Gy x 3 days will be tested.

Dose Calculations

Injection: 1200 mg/20 mL (60 mg/mL) colorless to slightly yellow solution in a single-dose vial.

For Advanced Urothelial Cancer: Atezolizumab is given every 3 weeks.

The recommended dose of Atezolizumab is 1200mg administered (flat dose) as an intravenous infusion over 60 minutes every 3 weeks until disease progression or unacceptable toxicity. If the first infusion is tolerated, all subsequent infusions may be delivered over 30 minutes. Do not administer Atezolizumab as an intravenous push or bolus.

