Eligible patients with metastatic renal cell and urothelial cancers must have at least two separate measurable sites of disease. Extent of metastatic disease is recorded by CT scanning or MRI. There are two cohorts of patients; patients with renal cell carcinoma and patients with urothelial cancers. Patients will be stratified into one of two cohorts (based on tumor type, renal cell carcinoma [cohort 1] or urothelial carcinoma [cohort 2]) and subsequently randomized to either immunotherapy without radiation (Arm A) or immunotherapy with radiation (Arm B).

In Arm A:

1. Patient with Renal Cell carcinoma will receive Nivolumab alone Days* 1, 15, 29, 43 and 57.
2. Patients with Urothelial cancer will receive either Nivolumab on Days* 1, 15, 29 43 and 57, or Atezolizumab or Pembrolizumab on Days* 1, 22, 43 and 64.

(* - infusions will have a \pm 3 days window to accommodate inevitable scheduling changes and holidays)

In Arm B:

1. Radiation is given to one lesion, 30 Gy in 3 fractions of 10 Gy each, over a one week interval (with a minimum of 36hrs between each fraction), conformally or by intensity modulated radiation treatment to maximally spare normal tissue. On the day of radiation (Day 1) immunotherapy is administered and repeated on the scheduled days. Patients will receive radiation on Day 1 and immunotherapy will be given \pm 24hr from Day 1.
2. Patient with Renal Cell carcinoma will receive Nivolumab alone Days* 1, 15, 29, 43 and 57.
3. Patients with Urothelial cancer will receive either Nivolumab alone on Days* 1, 15, 29,43 and 57 or Atezolizumab or Pembrolizumab on Days* 1, 22, 43 and 64.

(* - infusions will have a \pm 3 days window to accommodate inevitable scheduling changes and holidays)

Patients on both treatment arms will undergo re-imaging on Day 63 (\pm 7days), (Renal cell carcinoma patients should have received 5 doses; Urothelial Cancer patients should have received 3-4 doses) and every 9 weeks (\pm 7 days) for one year and every 12 weeks(\pm 7 days) thereafter.

1.10 7.0 Correlative studies

1.10.1.1 7.1 Evaluation of the cellular immune responses

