9.0 Study Therapy [Nivolumab]

9.1 Nivolumab

Nivolumab is a human monoclonal antibody that blocks the interaction between PD-1 and its ligands, PD-L1 and PD-L2. Nivolumab is an IgG4 kappa immunoglobulin that has a calculated molecular mass of 146 kDa. Binding of the PD-1 ligands, PD-L1 and PD-L2, to the PD-1 receptor found on T cells, inhibits T-cell proliferation and cytokine production. Upregulation of PD-1 ligands occurs in some tumors and signaling through this pathway can contribute to inhibition of active T-cell immune surveillance of tumors. Nivolumab is a human immunoglobulin G4 (IgG4) monoclonal antibody that binds to the PD-1 receptor and blocks its interaction with PD-L1 and PD-L2, releasing PD-1 pathway-mediated inhibition of the immune response, including the anti-tumor immune response. In syngeneic mouse tumor models, blocking PD-1 activity resulted in decreased tumor growth.

Patients with Renal cell carcinoma will receive Nivolumab intravenously at a flat dose of 240mg every two weeks. Infusions will be given over 60 minutes (not bolus or IV push).

In Arm A:

Patient with Renal Cell carcinoma will receive nivolumab alone Days* 1, 15, 29, 43 and 57.

(* - infusions will have a \pm 3 days window to accommodate inevitable scheduling changes and holidays)

In Arm B:

Radiation is given to one lesion, 30 Gy in 3 fractions of 10 Gy each, over one week interval (with a minimum of 36 hours between each fraction), conformally or by intensity modulated radiation treatment to maximally spare normal tissue.

On the day of radiation (Day 1) immunotherapy is administered and repeated on the scheduled days. Patients will receive radiation on Day 1 and immunotherapy will be given \pm 24hr from Day 1.

Patients on both treatment arms will undergo re-imaging on Day 63 (\pm 7 days) (after the first 5 doses of Nivolumab) and every 9 (\pm 7 days) weeks for one year and every 12 weeks (\pm 7 days) thereafter. The first dose will be administered on Day 1 (\pm 24hrs) and repeated on Days 15, 22, 43 and 57. Radiation will be delivered every other day (with a minimum of 36 hours between the fractions) preferably starting on a Monday. A dose of 10 Gy x 3 days will be tested.

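### Two dosing sentences list wrong infusion days: the list in 10.1 fits no study drug, and 9.1 puts nivolumab on Day 22 where Day 29 is due

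*Combined protocol and SAP*

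**What the plan says.** Section 10.1 first lists the Arm A days for urothelial patients: "either Nivolumab on Days* 1, 15, 29, 43 and 57 or Atezolizumab or Pembrolizumab on Days* 1, 22, 43, 64". Under its Arm B heading it describes the radiotherapy and adds: "On the day of radiation (Day 1) immunotherapy is administered and repeated on the scheduled days". A paragraph on re-imaging follows, which opens by referring to both arms. Next comes the sentence at issue, which names no drug: first dose on Day 1, "repeated on Days 15, 22, 43 and 64". Under Dose Calculations the same section says: "Atezolizumab is given every 3 weeks".

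Section 9.1 has the same layout. Its Arm A line puts nivolumab on Days 1, 15, 29, 43 and 57. The closing sentence below its Arm B heading has nivolumab "repeated on Days 15, 22, 43 and 57". Section 9.2 gives a two-week interval.

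Section 6.2 (Study Design) sets out the days for each arm and gives both arms the same ones. For urothelial patients in Arm B it reads: "Nivolumab alone on Days* 1, 15, 29,43 and 57 or Atezolizumab or Pembrolizumab on Days* 1, 22, 43 and 64". Renal patients in both arms have nivolumab on Days 1, 15, 29, 43 and 57.

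The procedure tables agree with 6.2. Section 15 (nivolumab) has columns for Days 15, 29, 43 and 57 and none for Day 22. Section 16 (atezolizumab/pembrolizumab) has columns for Days 22, 43 and 64 and none for Day 15. Their infusion rows are labelled Arm A, but the section titles cover treatment with and without radiation. The graphics of the Section 14 calendar are not in the text available for review, so they could not be checked.

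**The concern.** Sections 9 and 10 are the study-therapy sections, where staff would look up infusion days. Under each Arm B heading the wrong list is the only one that names days, because the phrase about scheduled days gives no dates of its own.

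Followed literally, 10.1 would add a 1,200 mg atezolizumab infusion one week before the Day 22 dose. Section 9.1 would move a nivolumab dose forward to Day 22 and leave no infusion on Day 29. Sections 7.2 and 15 require an immune-monitoring sample before the infusion on that day.

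**Working it through.** **Inputs.** Nivolumab every 14 days (9.2). Atezolizumab every 21 days (10.1). Pembrolizumab every 21 days (Protocol Summary). Infusion window ±3 days (6.2; footnote h in Sections 15 and 16). Atezolizumab 1,200 mg and nivolumab 240 mg, both flat doses.

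**Step 1: reproduce the intended schedule.**
- Every two weeks, day = 1 + 14k for k = 0 to 4: Days 1, 15, 29, 43, 57.
- Every three weeks, day = 1 + 21k for k = 0 to 3: Days 1, 22, 43, 64.

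Both match 6.2, the Arm A lines of 9.1 and 10.1, and the columns in Sections 15 and 16.

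**Step 2: compare the two printed lists.**

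| Printed list | Compared with | Off schedule | Missing |
|---|---|---|---|
| 10.1: 1, 15, 22, 43, 64 | every 3 weeks | 15 | none |
| 10.1: 1, 15, 22, 43, 64 | every 2 weeks | 22, 64 | 29, 57 |
| 10.1: 1, 15, 22, 43, 64 | both schedules merged | none | 29, 57 |
| 9.1: 1, 15, 22, 43, 57 | every 2 weeks | 22 | 29 |

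The 10.1 list fails against either schedule and also as a combined list for all three drugs.

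**Step 3: does the window help?** With ±3 days, Day 15 covers Days 12–18, Day 22 covers 19–25, Day 29 covers 26–32, Day 57 covers 54–60 and Day 64 covers 61–67. No two of these ranges overlap, so a dose on a wrong day cannot count as a dose on the right one.

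**Step 4: the literal consequences.**
- 10.1 read for atezolizumab: gaps of 14, 7, 21 and 21 days. Five infusions through Day 64 against four, or 5 × 1,200 = 6,000 mg against 4 × 1,200 = 4,800 mg (1/4 = 25% more over that period).
- 10.1 read for nivolumab: the same gaps of 14, 7, 21 and 21 days, where four gaps of 14 are intended.
- 9.1: gaps of 14, 7, 21 and 14 days. The total through Day 57 is unchanged at 5 × 240 = 1,200 mg, but there is no Day 29 infusion.

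**The case against.** The strongest reply is that the correct schedule appears many times elsewhere: in 6.2 with explicit Arm B lists, in the Arm A lines of the same two sections, in both procedure tables, and in sampling days that fit it. Section 10.1 itself states the three-week interval, which contradicts a Day 15 dose. A pharmacist reading the whole section would probably notice the conflict. This stands, and it is why the point is minor. It does not make the two lists correct.

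The arm that the sentences cover is also uncertain. They sit under Arm B headings but follow a paragraph about both arms. This too stands, but the lists are wrong on either reading.

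Two stronger inferences are tempting, and the documents support neither.
- A reader might infer that Arm B is meant to receive more, or differently timed, immunotherapy, which would confound the comparison of arms. Section 6.2 gives both arms identical immunotherapy days, and no text sets a separate Arm B schedule.
- A reader might infer that the Day 15 atezolizumab dose is deliberate. Section 10.1 places the Day 63 scan "after completing 4 doses of Atezolizumab", and the printed list gives exactly four doses before Day 63 (Days 1, 15, 22, 43). But the correct schedule can also give four: the scan may fall on Days 56–70 and the Day 64 dose on Days 61–67. Section 6.2 allows for this: "Renal cell carcinoma patients should have received 5 doses; Urothelial Cancer patients should have received 3-4 doses". The scan sentence in 10.1 is also garbled, possibly by text extraction, and cannot carry that inference.

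**Conclusion.** The two sentences are wrong as written. The error is minor and most likely a copying slip. In 10.1, Day 15 does not belong for atezolizumab or pembrolizumab, and the list does not serve nivolumab. In 9.1, Day 22 should be Day 29.

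The size is that of a literal reading: one extra atezolizumab infusion through Day 64, or one nivolumab dose given 7 days early with Day 29 left empty. It assumes that someone follows the sentence and ignores the interval and the other lists. A reader might go on to infer that patients were misdosed, or project the extra dose over longer treatment. The documents contain no dosing records, and treatment ends at progression or dose-limiting toxicity, so neither inference is supported. The number of patients exposed to the wording cannot be derived. The sample size, the one-sided 20% alpha, the stated power and the planned analysis do not depend on these sentences.

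**What to change.** In 10.1, write: *repeated on Days 22, 43 and 64 for atezolizumab or pembrolizumab (Days 15, 29, 43 and 57 if nivolumab is given, as in 6.2)*. In 9.1, write: *repeated on Days 15, 29, 43 and 57*.

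The nivolumab clause in 10.1 follows 6.2, the Schema and the section's own Arm A line. The Study Agent text of the Protocol Summary names only atezolizumab or pembrolizumab for urothelial patients, so the sponsor should confirm that nivolumab remains an option there before adopting the clause.

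The cost is two text corrections in one administrative amendment, with no change to design, sample size or analysis.
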